#### 4.2.2. Nonclinical Data

The IMR-687 nonclinical program for SCD supports its potential utility for the treatment of  $\beta$ -thalassemia.

In vitro studies have demonstrated IMR-687's ability to increase cGMP in K562 cells and increase HbF in both K562 and CD36+ RBCs cultured ex vivo from blood-derived CD34+ cells from SCD patients, supporting IMR-687's proposed mechanism of action. These findings were confirmed and extended by in vivo studies demonstrating IMR-687's ability to increase HbF and reduce RBC sickling in both Berkeley and Townes sickle cell transgenic mouse models and to reduce the degree of microvascular stasis observed following hypoxia and re-oxygenation in Townes mice. Administration of 10 or 30 mg/kg IMR-687 to C57Bl/6J mice for 5 days demonstrated low CNS exposure, with no effect on locomotor activity or memory.

In a series of GLP/OECD-compliant safety pharmacology studies evaluating behavioral, respiratory, and cardiovascular functions, no untoward adverse effects were noted. In addition, repeat-dose toxicology studies in rats (up to 6 months) and dogs (up to 9 months) were well tolerated and provided no observed adverse effect levels (NOAELs) that were comfortably in excess of those to be administered to humans.

IMR-687 had low-moderate plasma protein binding in the 5 species tested (<32%), and there was no notable partitioning into red blood cells (RBCs). IMR-687 has the potential for induction of CYP3A4 (half-maximal effective concentration  $[EC_{50}] = 32.4$  to  $133 \mu\text{M}$ ). IMR-687 was not a competitive inhibitor of CYPs 1A2, 2B6, 3A4/5, 2C9, 2C19, 2C8, and 2D6. IMR-687 is a substrate of P-glycoprotein (P-gp) ( $K_m > 500 \mu\text{M}$ ) and breast cancer resistance protein (BCRP) ( $K_m = 45.5 \mu\text{M}$ ). IMR-687 is an inhibitor of BCRP (half-maximal inhibitory concentration  $[IC_{50}] = 32.5 \mu\text{M}$ ), OCT1 ( $IC_{50} = 834 \mu\text{M}$ ), and MATE2-K ( $IC_{50} = 441 \mu\text{M}$ ).

Fifteen metabolites have been detected to date. Metabolic pathways included dehydrogenation, hydration, and oxidation. Both renal and biliary excretion of  $^{14}\text{C}$ -IMR-687-related radioactivity (as unchanged IMR-687 and metabolites) were observed in the rat. Metabolites found in rat hepatocytes were consistent with those observed in vivo. Metabolites in human hepatocytes were not unique relative to those observed in rat and dog hepatocytes. CYP phenotyping experiments have indicated that IMR-687 is primarily a substrate for CYP3A4 ( $K_m \approx 127 \mu\text{M}$ ). Metabolites M1 and M4 result from N-dealkylation of IMR-687 and may be major circulating metabolites.

#### 4.2.2.1. Nonclinical Data in $\beta$ -Thalassemia

Preliminary pharmacology studies of IMR-687 were conducted in a  $\beta$ -thalassemia intermedia animal model ( $\text{Hb}^{\text{th1/th1}}$  mice). This mouse model does not have functional  $\text{Hb}\beta$ , leading to deficits in Hb and RBCs and defective RBC maturation. IMR-687 administration led to a dose-dependent increase in total Hb (increase of 1.3 g/dL compared to placebo at the highest dose tested of 60 mg/kg). Total RBCs increased in a similar fashion and differences from placebo administration were statistically significant for both measures. IMR-687 also showed enablement of RBC maturation, a key mechanistic component in reducing disease pathology. High-dose IMR-687 (60 mg/kg) produced a statistically significant difference in immature RBCs (polychromatic erythroblasts) and greater prevalence of mature RBCs (orthochromatic and reticulocytes) compared to placebo administration.

Administration for 30 days of 30 mg/kg/day or 60 mg/kg/day of IMR-687 improves markers of  $\beta$ -thalassemia disease progression by increasing RBCs and Hb and reducing reticulocytes. The degree of these changes was dose dependent. In addition, IMR-687 at 60 mg/kg/day improved

erythroblast differentiation, suggesting a role for this compound in the improvement of ineffective erythropoiesis of  $\beta$ -thalassemia.

Additional information on the nonclinical effects of IMR-687 is provided in the Investigator's Brochure.

#### 4.2.3. Clinical Data

##### 4.2.3.1. Phase 1a Study of IMR-687 in Healthy Adult Volunteers (IMR-SCD-101)

A first-in-human, randomized, double-blind, placebo-controlled study to evaluate the safety, tolerability, and pharmacokinetics (PK) of IMR-687 (capsule formulation) has been completed (IMR-SCD-101). The study enrolled 66 healthy male and female adults (aged 18 to 55 years, inclusive), of whom 16 subjects received placebo and 50 subjects received IMR-687. The study was divided into 3 parts: a single-ascending-dose (SAD) study (Part A), a food effect study (Part B), and a multiple-ascending-dose (MAD) study (Part C); all parts had oral dosing. In Part A, 20 subjects received single doses of IMR-687 in the fasted state. The initial planned doses were 0.3, 1, 3, 6, 9, and 12 mg/kg; a 4.5 mg/kg dose was added and the 9 and 12 mg/kg doses were removed after a dose-limiting toxicity of moderate emesis was observed at 6 mg/kg. In Part B, 12 subjects received 2 single doses of IMR-687 at 1 mg/kg under fed and fasting conditions. In Part C, 18 subjects received 7 doses of either 1, 3, or 4.5 mg/kg/day.

IMR-687 was safe and well-tolerated at doses up to 4.5 mg/kg when administered as single and multiple once daily (qd) doses (up to 7 days) of oral capsules to healthy volunteers in a weight-based dosing regimen. The most frequent drug-related adverse event (AE) was nausea. In Part A (SAD study in the fasted state), 35% of all IMR-687 subjects experienced nausea, compared to 0% of placebo subjects. Nausea was mild, transient, and self-limited at doses  $\leq$ 4.5 mg/kg; the incidence of nausea was sporadic at single doses  $\leq$ 3 mg/kg IMR-687. Headaches were also a notable, likely drug-related treatment-emergent adverse event (TEAE), particularly in the fasted state (30% of all IMR-687 subjects in the SAD Part A, compared to 0% in the placebo group).

Oral administration of IMR-687 with food significantly reduced both the incidence and severity of the nausea and headache TEAEs. Whereas single doses of 4.5 mg/kg IMR-687 in fasted subjects resulted in mild nausea in 75% of subjects, single doses of 4.5 mg/kg IMR-687 did not result in nausea when given after a high-fat meal. Only after at least 6 daily doses did mild nausea occur with 4.5 mg/kg IMR-687 given with a meal. The incidence of headaches when IMR-687 was given with food was similar between IMR-687-treated (11.1%) and placebo-treated (16.7%) groups.

Nausea onset was between 30 and 120 minutes after the oral administration of IMR-687, and generally lasted 2 to 8 hours. Timing of nausea onset preceded/overlapped with the IMR-687 time to maximum concentration ( $t_{max}$ ). Together with the mitigating effects of food intake and the fact that IMR-687 is a P-gp substrate and unlikely to be CNS penetrant, these data are consistent with nausea/emeisis resulting from a local effect of IMR-687 in the stomach or the gastrointestinal (GI) tract.

IMR-687 administration was not associated with any clinically significant changes in laboratory values, physical examinations, or standard 12-lead electrocardiograms (ECGs). Of note,

IMR-687 did not demonstrate any significant changes in white blood cell (WBC), platelet, or absolute neutrophil counts.

Exposure parameters following single or multiple qd doses of IMR-687 increased with dose in a near dose proportional manner (e.g., a 4.1-fold increase for a 4.5-fold change in dose).

Administration with food slowed the rate of absorption of IMR-687 (median  $t_{max}$  delayed by approximately 3 hours), which resulted in an approximately 26% decrease in maximum plasma concentration ( $C_{max}$ ), but no change in overall exposure (area under the concentration-time curve [AUC]). Multiple dose PK demonstrated that IMR-687 did not accumulate to a significant extent in healthy volunteers (<13%). In addition, steady state was achieved prior to dosing on Day 3.

#### **4.2.3.2. Phase 2a Study of IMR-687 in Adult Subjects with Sickle Cell Anemia (IMR-SCD-102)**

Study IMR-SCD-102 was a phase 2a, randomized, double-blind, placebo-controlled study in adult subjects with homozygous HbSS or sickle- $\beta$ 0-thalassemia that was completed in 2020.

The objectives of this study were to evaluate the safety, tolerability, PK, and pharmacodynamic (PD) effects of IMR-687 (tablet formulation) administered for 16 to 24 weeks in 2 subject populations: those not on HU (Population A) and those receiving a stable dose of HU according to standard of care (Population B). Eligible subjects in non-HU Population A were initially randomized 1:1:1 to receive 50 mg IMR-687, 100 mg IMR-687, or placebo for a total of 24 weeks. A planned interim analysis suggested that the 50 mg dose would not provide the exposure and efficacy needed to meet clinical outcomes, and the protocol was amended for subjects to receive 100 mg IMR-687 or placebo in a 2:1 randomization for 4 weeks and, if well tolerated, to escalate from 100 mg to 200 mg for the remaining 20 weeks of the study. Similarly, in stable HU Population B, subjects were randomized 2:1 to receive 50 mg IMR-687 or placebo; following the planned interim analysis, subjects received 50 mg IMR-687 or placebo for 4 weeks and, if well tolerated, escalated from 50 mg to 100 mg for the remaining 20 weeks of the study.

A total of 93 subjects with SCD were enrolled, randomized, and received study drug (IMR-687 or placebo) in Study IMR-SCD-102 (58 subjects in Populations A/A1 and 35 subjects in Populations B/B1; 63 subjects received IMR-687 and 30 subjects received placebo). In summary, qd dosing of IMR-687 was generally safe and well tolerated. Additional information on the study results is provided in the Investigator's Brochure.

## 5. RATIONALE

### 5.1. Study Rationale and IMR-687 Dose Rationale

This is a phase 2 study intended to explore the potential use of IMR-687 to treat subjects with  $\beta$ -thalassemia. This is the first study of IMR-687 in a  $\beta$ -thalassemia population, and, as such, is designed to examine the safety, tolerability, and PK, as well as the potential PD effects, of IMR-687 administered qd for 36 weeks in adult subjects with  $\beta$ -thalassemia. The dose rationale is based on three important considerations as described below.

#### Nonclinical Safety and Efficacy

The NOAEs identified in repeat-dose toxicology studies were 100 mg/kg/day (600 mg/m^2/day) in male and female rats, 50 mg/kg/day (1000 mg/m^2) in male dogs, and 25 mg/kg/day (500 mg/m^2/day) in female dogs, which correspond to human equivalent doses (HEDs) of 16.2 and 13.5 mg/kg/day, respectively. These HEDs provide approximately 2-fold exposure margins based on body weight for the highest possible dose in the proposed clinical study (up to 6.7 mg/kg). Therefore, the dose exposure in this study is supported by the nonclinical program and considered safe for adult subjects. Additionally, administration for 30 days of 30 mg/kg/day (HED of 2.4 mg/kg/day) or 60 mg/kg/day (HED of 4.9 mg/kg/day) of IMR-687 in a  $\beta$ -thalassemia intermedia animal model (Hbbth1/th1 mice) improves markers of  $\beta$ -thalassemia disease progression by increasing RBCs and Hb, and reducing reticulocytes. The degree of these changes was dose dependent, with significant improvement at the higher dose of 60 mg/kg. In addition, IMR-687 at 60 mg/kg improved erythroblast differentiation, suggesting a role for this compound in the improvement of ineffective erythropoiesis of  $\beta$ -thalassemia. Testing a broader dose range in this program is justified by the nonclinical efficacy data observed.

#### Actual and Predicted Human Safety Margins of IMR-687 Doses

Clinical safety and tolerability data are available from Study IMR-SCD-101 in healthy volunteers for IMR-687 administered at doses up to 6 mg/kg/day in a fasted single ascending dose (SAD) portion (Part A) and at doses up to 4.5 mg/kg/day for 7 days in a fed multiple ascending dose (MAD) portion (Part C), as well as from the phase 2a study in fed SCD subjects (IMR-SCD-102). Based on these data, an exposure range from 3 mg/kg to approximately 6 mg/kg is expected to be tolerable, especially if taken with food because administration with food appears to reduce both the incidence and severity of GI-related TEAEs, such as nausea and upper GI pain.

The onset of nausea in the healthy volunteer study was rapid (between 30 to 120 minutes), generally lasted 2 to 8 hours, and was mild nature at doses  $\leq$ 4.5 mg/kg (lower dose). These potential AEs of nausea, upper GI pain, and emesis are easily monitorable and are self-limited if dosing is stopped. Furthermore, following qd dosing for 7 days in fed healthy volunteers, steady state was achieved before Day 7. Exposure (AUC) in healthy volunteers increased in a near dose-proportional manner (a 4.1-fold increase for a 4.5-fold change in dose [see Section 4.2.3.1]), and the mean exposure (AUC from time 0 to 24 hours [AUC0-24]) at 4.5 mg/kg on Day 7 was 26.3  $\mu$ g $\cdot$ h/mL, which is approximately 3.3-fold below the Week 39 exposure (AUC0-24) in the female dog (most conservative species/gender) at the respective NOAEL in the repeat-dose toxicology study. Even for the higher dose arm of up to 6.7 mg/kg (assumed to be equivalent to approximately a 400 mg dose), the predicted Day 1 exposure is 32.0  $\mu$ g $\cdot$ h/mL, which is

approximately 2.7-fold below the Week 39 exposure (AUC0-24) in the female dog (most conservative species/gender). PK plotting (e.g., concentration at 24 hours after study drug administration [C24]) predicted that higher exposure to IMR-687 should result in drug concentration levels above the estimated concentration at which inhibition is 90% (IC90) for approximately 22 hours at a 300-mg dose and more than 24 hours at a 400-mg dose. This possible IC90 advantage with respect to inhibition of the target, PDE9, further supports evaluating both the lower and higher doses of IMR-687 and specifically doses of up to 6.7 mg/kg, which can provide adequate target coverage to potentially improve clinical benefit.

### **Independent Data Monitoring Committee Oversight**

This study initially imposed a minimum weight threshold of 45 kg and a 67-kg weight gate for tablet strength to ensure that subjects in the lower dose IMR-687 group received a dose equating to no more than the 4.5 mg/kg evaluated in the MAD part of the healthy volunteer study. Subsequently, the Data Monitoring Committee (DMC) approved the opening of enrollment in the higher dose IMR-687 group (up to 6.7 mg/kg). Having established safety and tolerability of the lower dose, the DMC also approved a change in weight gate to 60 kg and the resultant modified dose range of up to 5.0 mg/kg in the lower dose group (with the minimum weight threshold of 45 kg unchanged). Starting from Protocol Version 5.0, subjects in the IMR-687 lower dose group will receive  $\geq 3.4$  to  $\leq 5.0$  mg/kg and subjects in the higher dose group will receive  $>5.0$  to  $\leq 6.7$  mg/kg; no subject will receive more than 6.7 mg/kg. Under Protocol Version 4.0, the exposure ranges were  $\geq 3.0$  to  $\leq 4.5$  mg/kg in the lower dose group and  $>4.5$  to  $\leq 6.7$  mg/kg in the higher dose group. Therefore, the overall exposure ranges during the course of the study are  $\geq 3.0$  to  $\leq 5.0$  mg/kg and  $>4.5$  to  $\leq 6.7$  mg/kg and are presented as such hereafter.

For this first study evaluating IMR-687 in subjects with  $\beta$ -thalassemia, the DMC has noted some of the related pathology that is shared with patients who have SCD. The shared manifestations include chronic anemia, fatigue, delayed growth, cerebral ischemia, splenomegaly, gallstones, pulmonary hypertension, and leg ulcers. In the phase 2a study in adult subjects with SCD (IMR-SCD-102), IMR-687 has been shown to be well tolerated, with initial evidence of PD effects. The DMC has reviewed interim results from this study and is supportive of the dose exposure and duration of treatment in this first  $\beta$ -thalassemia study.

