### **Study Design (Methodology):**

This is a phase 2, randomized, double-blind, placebo-controlled study to evaluate the safety, tolerability, PK, and PD of IMR-687 (phosphodiesterase (PDE) 9 inhibitor) administered once daily (qd) for 36 weeks in 2 populations of adult subjects with β-thalassemia: Population 1 (TDT subjects) and Population 2 (NTDT subjects). A schematic of the study is provided in Section 7 of the protocol.

This study will enroll approximately 120 subjects with β-thalassemia (60 subjects with TDT and 60 subjects with NTDT), aged 18 through 65 years. This study consists of a retrospective data collection period, a screening period, a double-blind treatment period, and a safety follow-up period. During the screening period of up to 28 days, subjects will provide informed consent and be evaluated on eligibility criteria as stated below.

Subjects will receive either IMR-687 (lower dose [ $\geq 3.0$  to  $\leq 5.0$  mg/kg] or higher dose [ $>4.5$  to  $\leq 6.7$  mg/kg]; the precise exposure ranges for different groups of subjects are dependent on the weight gate for tablet strength as summarized under Study Rationale below) or placebo in a blinded fashion. Subjects will be randomly assigned in a 2:1 ratio to receive either IMR-687 lower dose or placebo. Prior to the introduction of IMR-687 higher dose, the Data Monitoring Committee (DMC) will review safety data for at least 5 subjects who received IMR-687. If the DMC recommends inclusion of the higher dose, randomization will then proceed in a 1:2:1 ratio (IMR-687 lower dose, IMR-687 higher dose, or placebo). The DMC may request additional data and/or meeting(s) in order to make the recommendation on whether to move forward with inclusion of the higher dose. During study conduct under Protocol Version 4.0, the DMC approved the opening of enrollment in the higher dose IMR-687 group, which went into effect on 01 February 2021.

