### **5.2. Benefit/Risk Assessment**

IMR-687 is currently being investigated for the treatment of SCD as its primary indication. It is anticipated that it will differ from established therapy (i.e., HU) in maintaining a similar or improved efficacy profile, while having a much-improved safety profile, without myelosuppression or a mutagenicity/carcinogenicity risk.

Consequently, the frequent monitoring of blood counts required for patients who use HU would not be required for IMR-687. The proposed exposure in this study is between  $\geq 3.0$  to  $\leq 5.0$  mg/kg (lower dose) daily and, following DMC approval,  $>4.5$  to  $\leq 6.7$  mg/kg (higher dose) daily; these exposures are anticipated to be in the pharmacologically active range based on available nonclinical and clinical data (see Section 5.1 for dose selection rationale). Based on the observed safety and tolerability of IMR-687 in the first-in-human study (Section 4.2.3.1) and subsequent study in SCD subjects, these dose levels should be tolerable and may have a clinically beneficial PD effect in subjects with  $\beta$ -thalassemia.

Based on the data from healthy volunteers and SCD subjects to date, IMR-687 is considered to be safe and well tolerated with the most common side effects being sickle cell anemia with crisis, abdominal pain, nausea, headache, indigestion, diarrhea/loose stools, and influenza-like illness which are mild and easily managed. Newly emerging safety data will be updated in the Investigator Brochure's (IB) and Informed Consent Form (ICF). The potential benefits and risks are summarized below.

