### 5.2.2.3. Cardiovascular

In nonclinical safety pharmacology and 14-day GLP toxicology studies in beagle dogs, IMR-687 appeared to result in increases in heart rate that did not appear to be dose dependent. In the safety pharmacology study in dogs, at doses of 75 mg/kg, statistically significant changes in heart rates were observed. In the 14-day toxicology study in dogs, the highest heart rates were noted at the highest dose level of 75 mg/kg but did not reach statistical significance. In a subsequent 9-month study in dogs at doses up to and including 50 mg/kg/day, there was no evidence of any increases in heart rate and there were no histopathological abnormalities noted in cardiac tissue. In healthy volunteers in the first-in-human study, at doses between 0.3 to 6 mg/kg, sporadic observations of sinus tachycardia (i.e., heart rates >100 bpm) occurred in various subjects, including a subject in the MAD on placebo. The contribution of concomitant AEs such as headache to the rise in heart rate could not be excluded. No dose dependency or dose-duration dependency was noted for these heart rate observations. No signs of prolongation of corrected QT interval, Fridericia's formula (QTcF) were noted in any cohort of healthy volunteers at any dose of IMR-687. In the interim safety analysis of Study IMR-SCD-102, with respect to vital signs, there were no observable changes in systolic, diastolic blood pressure and pulse, and there were no changes in respiratory rate. In the IMR-SCD-102 clinical study, the mean interim steady state AUC0-24 was 16,300 ng•hr/mL for the 200 mg (~2.9 mg/kg) IMR-687 dose level. In the 39-week dog toxicology study mentioned above, mean AUC0-24 was ≥87,500 ng•hr/mL at the NOAEL in female dogs, resulting in safety margins of at least ~5.3-fold for the 200 mg clinical dose.

Monitoring of vital signs is recommended for subjects in IMR-687 studies. In the event of noted persistent and/or clinically significant tachycardia, other causes of tachycardia, particularly pain and dehydration, should also be considered.

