### 5.2.3. Potential Interactions

In vitro studies indicate that IMR-687 is not expected to competitively inhibit the major human cytochrome P450 (CYP) enzymes, including CYPs 3A4, 2D6, 2C9, 2C19, 2C8, 1A2, and 2B6. IMR-687 does have the potential for induction of CYP3A4/5 (in vitro EC50 = 32.4 to 133 μM) and other drug metabolizing enzymes whose expression levels are also controlled by the pregnane X receptor (PXR). In addition, IMR-687 has been shown to primarily be a CYP3A4 substrate (Km = 127 μM); IMR-687 may be at least partially cleared as unchanged drug.

After oral administration, concentrations of IMR-687 at the target exposure of ≥3.0 to ≤5.0 mg/kg for the lower dose or >4.5 to ≤6.7 mg/kg for the higher dose may reach sufficient exposure in the gastric mucosa and/or the liver (during absorption) to induce (upregulate) CYP3A4 and/or CYP3A5 protein expression in these organs.

Induced expression levels of CYP3A4 and CYP3A5 may not return to baseline levels until after discontinuation of IMR-687 dosing, which is likely to require approximately 1 week of washout due to the CYP3A protein half-life. Consequently, if a subject in this study is started on a medication that is primarily metabolized (and cleared) by CYP3A4/5, the subject should be followed appropriately to determine if the exposure to the concomitant medication is maintained at levels sufficient for efficacy. For example, if a subject is started on oxycodone for pain management or ondansetron for nausea, symptom resolution should be followed to determine if

higher doses of either medication are required to reach target outcomes, as co-administration of IMR-687 may result in a reduction in the overall exposure to oxycodone or ondansetron.

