## 7. INVESTIGATIONAL PLAN

### 7.1. Overall Study Design

This is a phase 2 randomized, double-blind, placebo-controlled study to evaluate the safety, tolerability, PK, and PD of IMR-687 (PDE9 inhibitor) administered qd for 36 weeks in 2 populations of adult subjects with  $\beta$ -thalassemia: Population 1 (TDT subjects) and Population 2 (NTDT subjects). A schematic of the study is provided in [Figure 1](#).

[figure not shown]
This study will enroll approximately 120 subjects with  $\beta$ -thalassemia (60 subjects with TDT and 60 subjects with NTDT), aged 18 through 65 years. This study consists of a retrospective data collection period, a screening period, a double-blind treatment period, and safety follow-up period. During the screening period of up to 28 days, subjects will provide informed consent and be evaluated on eligibility criteria as stated in [Section 8.1](#) and [Section 8.2](#).

Subjects will receive either IMR-687 (lower dose [ $\geq 3.0$  to  $\leq 5.0$  mg/kg] or higher dose [ $>4.5$  to  $\leq 6.7$  mg/kg]; the precise exposure ranges for different groups of subjects are dependent on the weight gate for tablet strength as summarized in [Section 5.1](#)) or placebo in a blinded fashion. Subjects will be randomly assigned in a 2:1 ratio to receive either IMR-687 lower dose or placebo. Prior to the introduction of IMR-687 higher dose, the DMC will review safety data for at least 5 subjects who received IMR-687. If the DMC recommends inclusion of the higher dose, randomization will then proceed in a 1:2:1 ratio (IMR-687 lower dose, IMR-687 higher dose, or placebo). The DMC may request additional data and/or meeting(s) in order to make the recommendation on whether to move forward with inclusion of the higher dose. During study conduct under Protocol Version 4.0, the DMC approved the opening of enrollment in the higher dose IMR-687 group, which went into effect on 01 February 2021.

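### The lower limits of the stated mg/kg dose ranges do not follow from the dispensing rule

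*Protocol*

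**What the plan says.** Protocol 5.1, under Independent Data Monitoring Committee Oversight, gives three pairs of ranges:

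| Period | Lower dose (mg/kg) | Higher dose (mg/kg) |
|---|---|---|
| Version 4.0 | 3.0 to 4.5 | above 4.5 to 6.7 |
| Version 5.0 onward | 3.4 to 5.0 | above 5.0 to 6.7 |
| Whole study | 3.0 to 5.0 | above 4.5 to 6.7 |

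The Version 5.0 pair is stated as fact: "Starting from Protocol Version 5.0, subjects in the IMR-687 lower dose group will receive" the range shown. The synopsis repeats it.

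The same section records that the tablet-strength cut-off has changed: "This study initially imposed a minimum weight threshold of 45 kg and a 67-kg weight gate for tablet strength". The cut-off is now 60 kg. Protocol 9.2 and SAP 8.0 give the current rule, two tablets a day:

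- Lower arm: 200 mg daily below 60 kg, 300 mg at 60 kg or more.
- Higher arm: 300 mg daily below 60 kg, 400 mg at 60 kg or more.

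Protocol 8.2 excludes weight below 45 kg and BMI above 35, and sets no maximum weight. SAP 13.3.1 fixes the dose level from baseline weight for the whole trial.

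The whole-study ranges recur in the synopsis, in Protocol 5.2 ("The proposed exposure in this study is between" those limits), in 5.2.3 ("After oral administration, concentrations of IMR-687 at the target exposure of" those limits) and in 7.1. SAP 8.0 pairs the Version 5.0 lower-dose range with the whole-study higher-dose range. SAP 13.3.1 uses the whole-study range for both arms but describes only the 60 kg cut-off.

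**The concern.** At and above the cut-off the daily dose is constant, so mg/kg falls steadily as weight rises. With no maximum weight, the rule cannot guarantee any minimum mg/kg, yet the protocol states minima for both arms.

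At stake is the description of dose in a two-dose study whose primary objective is safety and tolerability. The Version 5.0 ranges meet at 5.0 mg/kg and show no overlap between arms. Anyone relating adverse events or response to mg/kg would assume a separation that the rule does not deliver.

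**Working it through.** **Formula.** mg/kg = daily dose (two tablets × strength) ÷ body weight. Doses and the 60 kg cut-off are from Protocol 9.2 and SAP 8.0; the 45 kg minimum and BMI limit of 35 are from Protocol 8.2.

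**Stated upper limits.** These reproduce.

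- Lower arm: 200/45 = 4.44 and 300/60 = 5.00, so the maximum is 5.0.
- Higher arm: 300/45 = 6.67 and 400/60 = 6.67, so the maximum is 6.7.

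**Stated lower limits.** These reproduce only from the weight band just below the cut-off.

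- Version 5.0, lower arm: 200/59 = 3.39, which rounds to 3.4.
- Version 5.0, higher arm: 300/59.9 = 5.008, which is above 5.0.
- Version 4.0 (67 kg cut-off, same tablets assumed): 200/67 = 2.99 and 300/67 = 4.48, which round to 3.0 and 4.5.

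The open-ended band at and above the cut-off appears to have been left out.

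**Weight at which each lower limit is reached above the cut-off** (dose ÷ limit):

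| Stated limit | Calculation | Result |
|---|---|---|
| Higher arm, above 5.0 (Version 5.0) | 400/5.0 | fails from 80 kg |
| Higher arm, above 4.5 (whole study) | 400/4.5 | fails from 88.9 kg |
| Lower arm, at least 3.4 (Version 5.0) | 300/3.4 | fails above 88.2 kg |
| Lower arm, at least 3.0 (whole study) | 300/3.0 | fails above 100 kg |

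**Dose at selected weights under the Version 5.0 rule:**

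| Weight (kg) | Lower arm (mg/kg) | Higher arm (mg/kg) |
|---|---|---|
| 69 | 300/69 = 4.35 | 400/69 = 5.80 |
| 80 | 300/80 = 3.75 | 400/80 = 5.00 |
| 90 | 300/90 = 3.33 | 400/90 = 4.44 |
| 100 | 300/100 = 3.00 | 400/100 = 4.00 |
| 110 | 300/110 = 2.73 | 400/110 = 3.64 |

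**Rounding.** To one decimal, the dose is still below the limit at 400/80.9 = 4.944 (4.9), 400/89.9 = 4.449 (4.4), 300/89.6 = 3.348 (3.3) and 300/101.7 = 2.9499 (2.9).

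**Just below the cut-off.** From 58.9 to under 60 kg on 200 mg the dose runs from 3.40 down towards 3.33, at most 0.07 mg/kg short of 3.4.

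**Eligibility of these weights.** BMI 35 is reached at height √(weight/35): about 1.51 m for 80 kg, 1.59 m for 88.9 kg and 1.69 m for 100 kg. Taller subjects of those weights qualify. At 80 kg, BMI is 27.7 at 1.70 m and 24.7 at 1.80 m.

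**Overlap.** A 90 kg higher-dose subject gets 4.44 mg/kg, the same as a lower-dose subject of 45 kg (200/45) or 67.5 kg (300/67.5), and less than a lower-dose subject of 60 kg (5.00).

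**SAP 13.3.1.** Total exposure is tablets taken × tablet strength. If strength is inferred from baseline weight with the 60 kg cut-off, a subject of 60 to under 67 kg dosed under the 67 kg cut-off gets the wrong strength: 300 mg instead of 200 mg in the lower arm (300/200 = 1.5 times too high), and 400 mg instead of 300 mg in the higher arm (400/300 = 1.33 times). This assumes the same tablets were used then.

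**The case against.** The best defence is that the mg/kg ranges are only labels. Dispensing goes by arm and weight band, and that rule is clear. The synopsis and Protocol 7.1 say that "the precise exposure ranges for different groups of subjects are dependent on the weight gate for tablet strength as summarized in" Section 5.1, so the ranges need not be read as guarantees. Protocol 5.2 and 5.2.3 speak of proposed and target exposure, and Protocol Table 4 allows a one-tablet reduction, which halves the dose. The pharmacological rationale is in fixed doses: time above IC90 is put at "approximately 22 hours at a 300-mg dose and more than 24 hours at a 400-mg dose". At any given weight the higher arm receives 1.5 times (below 60 kg) or 1.33 times (60 kg or more) the lower-arm dose, so the arms stay separated. The whole-study ranges openly overlap between 4.5 and 5.0. Actual tablets, mg/day, baseline weight and plasma concentrations are all recorded.

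Most of this stands, and it limits the consequence. It does not supply a floor. The cross-reference leads to the very text in Section 5.1 that says what subjects will receive, and nothing there mentions that mg/kg keeps falling above the cut-off. The whole-study lower limits fail too, so their overlap is understated. Two components are slight: the miss just below 60 kg is close to rounding, and at exactly 80 kg the limit fails only on the strict inequality.

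Frequency is a fair point. The one hint is the sickle cell study in Protocol 5.2.2.3, where mean exposure is given "for the 200 mg (~2.9 mg/kg) IMR-687 dose level". That implies 200/2.9 = 69 kg, a weight at which all the stated ranges hold, but it is a different population.

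**Conclusion.** Wrong as written, and minor. Both the Version 5.0 and the whole-study lower limits fail at eligible adult weights; both upper limits hold at baseline weight, including the 6.7 mg/kg ceiling. At 90 kg the higher arm is 0.56 mg/kg under its Version 5.0 limit (5.0 − 4.44) and the lower arm 0.07 under (3.4 − 3.33).

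No overdose concern arises, comparisons by randomized arm are unaffected, and no endpoint, analysis set or safety cap uses the lower limits. What is affected is the reported dose range by arm and the apparent separation between arms, together with the exposure summary for some Version 4.0 subjects if SAP 13.3.1 is applied literally.

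The arithmetic needs no assumption for Version 5.0. Statements about the 67 kg period assume unchanged tablet strengths, which the documents do not confirm. The heights used above are illustrative.

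**What to change.** 1. Describe the arms by daily dose, 200/300 mg and 300/400 mg, as the table headers in SAP Appendix 6 already do, and keep only the mg/kg upper limits. Alternatively, give mg/kg by weight stratum for Version 5.0, with no lower limit at or above 60 kg:

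| Arm | 45 to <60 kg | 60 kg or more |
|---|---|---|
| Lower | 200 mg: 4.44 down to 3.33 | 300 mg: 5.0 and falling with weight |
| Higher | 300 mg: 6.67 down to 5.0 | 400 mg: 6.67 and falling with weight |

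2. Make the synopsis, Protocol 5.1, 5.2, 5.2.3 and 7.1, and SAP 8.0 and 13.3.1 agree, and mention the 67 kg cut-off in SAP 13.3.1.

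3. Add actual baseline mg/kg (daily dose ÷ baseline weight) by arm to the SAP 13.3.1 exposure table. Take the strength from what was dispensed, not from the 60 kg rule, so that subjects enrolled under the 67 kg cut-off are described correctly.

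The cost is wording in both documents, one derived variable and one group of rows in an existing table.
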